7.3.4 Medical History

A complete medical and surgical history will be collected at the screening visit. The medical and surgical history will be coded using the Medical Dictionary for Regulatory Activities (MedDRA; Version 19.1 or Higher).

Medical and surgical history will be summarized for the Safety Analysis Sets for Part A and Part B by system organ class and preferred term for each dose level groups and placebo and overall.

For Part A and Part B, all medical/surgical history will be presented in by-subject listings for all randomized subjects.

7.3.5 Prior and Concomitant Medications

Prior and concomitant medications will be coded using the World Health Organization (WHO) Drug Dictionary (October 2016 or later). Prior medications are defined as medications that were taken prior to and stopped before the first dose of the study medication. Concomitant medications are defined as medications that were taken on or after the first dose date of the study medication.

The number and percentage of subjects taking concomitant medications will be summarized by anatomic therapeutic class (ATC) and preferred term. Data will be presented by dose level and placebo for the Safety Analysis Sets in Part A and Part B. In addition, for Part B, concomitant medications will also be summarized in the same manner by dose level of ALN-GO1 using combined data from both the blinded portion and the open-label portion.

For Part A and Part B, prior and concomitant medications will be presented in by-subject listings.

7.4 Safety Analysis

The primary objective of the study is to assess the safety and tolerability of ALN-GO1 in healthy adult subjects and patients with a confirmed diagnosis of PH1. Safety analyses will include the summarization of Adverse Events (including Serious Adverse Events and Treatment-Emergent Adverse Events), exposure to study drug, vital signs, physical examination findings, ECG parameters, echocardiograms (Part B only), clinical laboratory assessments, and other safety variables. All safety analyses will be based on the Safety Analysis Sets.

7.4.1 Adverse Events

In Part A, summary tables for AEs will be presented by ascending ALN-GO1 dose level, in total with all subjects receiving ALN-GO1, and placebo with subjects/patients receiving placebo pooled across enrollment cohorts presented first. AEs will be summarized separately for the single-blind dosing period and the study.

In Part B, for patients who were randomized to placebo, an AE during the single-blind period is defined as an AE with onset date/time on and after the first dose date/time of placebo and prior to the first dose date/time of open-label ALN-GO1. For patients who were initially randomized to ALN-GO1 a AE during the single-blind period is defined as an AE with onset date/time on or after the first dose date/time of ALN-GO1 and up to, and including, Study Day 85. AEs for single-blind period will be summarized by regimen and ascending dose level of ALN-GO1 and pooled placebo across regimen and dose being presented first. Sub-total for each regimen and overall will also be presented.

In Part B, a summary of AEs for the single-blind period will be provided by regimen and ascending dose level of ALN-GO1 and pooled placebo presented first. Total for each regimen and overall of ALN-GO1 will also be provided.

In Part B, for all patients receiving ALN-GO1, either as single-blind or open-label administration, and in any sequence, a AE is defined as an AE with onset date/time on or after the first dose date/time of ALN-GO1 and up to the end of study. All AEs under ALN-GO1 will be summarized by regimen and ascending dose, sub-total for each regimen, and for overall. At each dose level and for the sub-total and overall, AEs with be summarized for patients with single-blind administration only and then for single-blind and open-label administration combined.

In each analysis above, an overview of adverse events will be provided which summarizes subject-level incidence (frequency) of all AEs, drug-related AEs, grade 3/4/5 AEs, drug-related grade 3/4/5 AEs, treatment-emergent SAEs, drug-related treatment-emergent SAEs, and AEs leading to discontinuation of study drug and/or deaths.

The number and percentage of subjects with AEs will be summarized by system organ class and preferred term. Drug-related AEs, grade 3/4/5 AEs, drug-related grade 3/4/5 AEs, treatment-emergent SAEs, drug-related treatment-emergent SAEs, AEs leading to discontinuation of study drug, AEs leading to study drug dose interruption and drug-related AEs leading to discontinuation of study drug will be summarized by system organ class and preferred term. For these summaries, subjects with multiple adverse events will be counted only once per SOC and preferred term. Summaries of AEs leading to discontinuation of study drug and leading to study drug dose interruption will be presented as applicable for the single-blind period, ALN-GO1 dosing period, and ALN-GO1 quarterly dosing period. Other summaries will be presented separately for the time periods in Sections 7.2.1 and 7.2.2.

In addition, summaries will be provided by the worst NCI-CTCAE grade, system organ class and preferred term for the number and percentage of subjects with AEs and drug-related AEs.

Listings will be provided for AEs leading to deaths, SAEs, and AEs leading to discontinuation of study drug or dose interruption.

By-subject AE data listings which will include at a minimum, subject/patient identifier, study drug taken prior to or on an AE onset date/time, verbatim term, preferred term, system organ class, NCI-CTCAE grade, relationship to study drug, action taken with study drug, SAE classification (Yes/No) and AE onset and end date/time. In addition, for Part A, AE and study day will also be included. In Part B, classification (yes/no) as a AE during the single-blind dosing period and the ALN-GO1 dosing period will be included. In Part B, study day and day relative to ALN-GO1 dosing will be included.

By-subject AE listings will be provided for Part A and Part B separately.

7.4.2 Dosing and Extent of Exposure

The actual dose administered and the number of injections will be summarized descriptively by dose level (or placebo) and overall for the Safety Analysis Set in Part A. Compliance with study drug administration is not relevant as all doses will be administered by qualified clinical study site personnel and recorded on the electronic Case Report Form.

Part B consists of three doses of study drug on Days 1, 29, and 57 for monthly dosing cohorts. For patients who randomized to placebo and crossed over to ALN-GO1 during the open label portion, study drug will be administered on Days 85, 113, and 141. Patients who randomized to receive ALN-GO1 will receive study treatment in a single-blind manner while patients enrolled in expansion cohorts will receive ALN-GO1 in an open-label manner.

In Part B for quarterly dosing cohorts, patients will receive either ALN-GO1 or placebo according to the randomized treatment assignment on Day 1. All patients in quarterly dosing cohorts, including those randomized to placebo, will receive open-label ALN-GO1 on Day 85 at the same dose administered to the cohort into which they were initially randomized.

Treatment duration of study drug in Part B is defined as:

- For patients randomized to placebo in monthly or quarterly cohorts, treatment duration of placebo is min (first dose date of open-label ALN-GO1 or visit date of Day 85 visit) – first dose date of placebo +1
- For patients in monthly dosing regimen, treatment duration of ALN-GO1 is the visit date of Day 85 relative to first dose of ALN-GO1 first dose date of ALN-GO1 +1
- For patients randomized to placebo in quarterly dosing cohorts, their treatment duration of open-label ALN-GO1 is the same as for monthly dosing regimen.

• For patients randomized to ALN-GO1 in quarterly dosing cohorts, the single-blind treatment duration is Day 85 visit date – first dosed date of ALN-GO1 +1 and the total ALN-GO1 treatment duration is Day 169 visit date – first dose date of ALN-GO1 +1.

Treatment duration of study drug will be summarized using descriptive statistics by regimen, ascending dose level of ALN-GO1, pooled placebo, and in total for the single-blind time period and total ALN-GO1 dosing period.

In Part B, dosing status will be tabulated by regimen and dose level (including placebo during the summary for the single-blind study period). The following categories will be summarized:

- Subjects with a missed dose,
- Subjects with a dose interruption

The above summary will be provided in Part B for the single-blind dosing period by pooled placebo, regimen, and ascending ALN-GO1 dose. The above summary will be provided separately for the ALN-GO1 dosing period (by regimen and ascending ALN-GO1 dose, regardless of treatment sequence) and ALN-GO1 quarterly open-label dosing period.

In Part A and Part B, all study drug administration information will be listed.

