4.3 General Statistical Considerations

The primary goal of the study is to evaluate the safety and tolerability of ALN-GO1 in healthy adult subjects and patients diagnosed with PH1. The data cutoff date for the primary analysis will occur after all subjects have either discontinued the study or completed all safety follow-up assessments (as in Section 3.2).

Continuous data will be described using descriptive statistics including the number of observations (n), mean, standard deviation, median, minimum, and maximum. Categorical and ordinal data will be described using the subject/patient count and percentage in each category. For the summary statistics of all numerical variables unless otherwise specified, minimum and maximum will be displayed to the same level of precision as reported. Mean, median, and standard deviation will be displayed to one level of precision greater than the data collected. Summary tables will present results by cohort for each ALN-GO1 dose in ascending dose order, total (all subjects receiving ALN-GO1), and placebo, where the placebo subjects/patients will be

combined across dose cohorts. Data will be displayed in all listings sorted by study part and cohorts with placebo ordered last.

Subjects/patients will be identified in the listings by the subject/patient identification number concatenated with the investigator number.

When count data are presented, the percentage will not be presented when the count is zero in order to draw attention to non-zero counts. A row denoted "Missing" will be included in tabulations where specified on the shells to account for dropouts and missing values. The denominator for all percentages will be the number of non-missing values in that cohort/treatment, unless otherwise specified.

If the assessment date is after the date of first study drug dose The study day will be calculated as:

Study day = Date of assessment – date of first dose of study drug + 1,

otherwise if assessment date is before the date of the first dose of study drug then study day will be calculated as:

Study day = Date of assessment - date of first study drug dose.

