4.3.4 Missing Data

Unrecorded data values will be recorded as missing. Only recorded (i.e. non-missing) data values will be used for reporting of descriptive statistics unless otherwise stated.

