7.2.3 By-visit Data Presentation

In Part B, the by-visit PD and safety summaries will be presented according to the specifications below.

Monthly Dosing Regimen: Part B

Timepoint ^a	Placebo ^b	Monthly	Monthly	Monthly	Monthly	Monthly	Monthly
	(N=4)	ALN-GO1	ALN-GO1	ALN-GO1	ALN-GO1	ALN-GO1	ALN-GO1
		Single-blind ^c	Comb.d	Single-blind ^c	Comb.d	Single-blind ^c	Comb.d
		Dose1	Dose1	Dose2	Dose2	Total	Total
		(N=3)	(N=4 or 8)	(N=3)	(N=4 or 8)	(N=6)	(N=8 or 16)
Baselinee							
Day 29							
Day 57							
Day 85 ^f							
Day 113	NA						
Day 141	NA						
Day 169 ^g	NA						
Day 197 ^h	NA						
Day 225	NA						
Day 253	NA						
Day 281	NA						
Day 309	NA						

- a: In monthly dosing regimen, patients randomized to ALN-GO1 will be summarized by study day 1 to 85 during the single-blind monthly treatment period, then by post dosing follow-up period after Day 85 and up to Day 169, followed by Safety and PD follow-up after Day 169. Patients randomized to Placebo will be summarized by study day 1 to 85 relative to placebo dosing date during the single-blind treatment period. Data collected after the first dose of ALN-GO1 will be summarized separately by days relative to the first open-label ALN-GO1 dose with all visits for the rest of the study mirrored to the patients randomized to the single-blind ALN-GO1. These data will be summarized in combination with data from patients randomized to ALN-GO1 at each corresponding visit.
- b: Patients from all monthly and quarterly dosing cohorts randomized to placebo at study start
- c: Patients randomized to ALN-GO1 at study start receiving ALN-GO1 in single-blind manner
- d: Patients receiving ALN-GO1 in single-blind or open-label manner and in any sequence combined
- e: Baseline is defined as before first dose date/time of each treatment, placebo or ALN-GO1
- f: Day 85 is the end of treatment period
- g: Day 169 is the end of post-treatment follow-up period
- h: Day 197 and later visits are Safety and PD follow-up visits

Quarterly Dosing Regimen: Part B

Timepointa	Placebob	Quarterly	Quarterly	Quarterly	Quarterly	Quarterly	Quarterly	Quarterly	Quarterly	Quarterly
	(N=4)	2-doses ^c	1-dose ^d	Comb.e	2-doses ^c	1-dose ^d	Comb.e	2-doses ^c	1-dose ^d	Comb.e
		ALN-GO1	ALN-GO1	ALN-GO1	ALN-GO1	ALN-GO1	ALN-GO1	ALN-GO1	ALN-GO1	ALN-GO1
		Dose1	Dose1	Dose1	Dose2	Dose2	Dose2	Total	Total	Total
		(N=3)	(N=1)	(N=4)	(N=3)	(N=1)	(N=4)	(N=6)	(N=2)	(N=8)
Baselinef										
Day 29										
Day 57										
Day 85g										

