Day 113 ^h	NA			NA			NA			NA
Day 141	NA			NA			NA			NA
Day 169 ⁱ	NA			NA			NA			NA
Day 197 ^j	NA			NA			NA			NA
Day 225	NA			NA			NA			NA
Day 253	NA			NA			NA			NA
Day 281	NA			NA			NA			NA
Day 309	NA			NA			NA			NA

- a: In quarterly dosing regimen, patients randomized to ALN-GO1 will be summarized during the treatment period by study days with ALN-GO1 dosing on Day 1 (single-blind) and 85 (open-label) followed by the Safety and PD follow-up period after Day 169. Patient randomized to Placebo will be summarized by days relative to placebo dosing date for the placebo period (Study Days 1-85), and separately by days relative to the open-label ALN-GO1 dosing date for the treatment period (Days 85-169 post placebo dose; Days 1-85 post ALN-GO1 dose), followed by the Safety and PD follow up period after Day 169.
- b: Patients from all monthly and quarterly dosing cohorts randomized to placebo at study start
- c: Patients randomized to ALN-GO1 at study start. First quarterly GO1 dose is in single-blind manner and the second quarterly GO1 dose is in open-label manner
- d: Patients randomized to placebo at study start and received one dose of open-label ALN-GO1 on Day 85, and Days are relative to the open label ALN-GO1 dose.
- e: Patients receiving ALN-GO1 in single-blind or open-label manner and in any sequence combined.
- f: Baseline is defined as xxxx before first dose date/time of each treatment, placebo or ALN-GO1
- g: Day 85 is the end of single-blind treatment period for placebo and 2-doses ALN-GO1 patients, and the end of open-label ALN-GO1 treatment period for 1-dose ALN-GO1 patients
- h: Day 113 and later visits are Safety and PD follow-up period for 1-dose ALN-GO1 patients
- i: Day 169 is the end of open-label treatment period for 2-doses ALN-GO1 patients
- j: Day 197 and later visits are Safety and PD follow-up period for 2-doses ALN-GO1 patients

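### Part B treatment duration takes no account of doses received: patients who stop multi-dose treatment but keep attending show the full 85 or 169 days, and a patient without the end visit has no stated end date

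*SAP*

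**What the plan says.** SAP 7.4.2 computes Part B duration as end date − first dose date + 1, with these end dates:

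- Monthly ALN-GO1, blinded or open-label: "treatment duration of ALN-GO1 is the visit date of Day 85 relative to first dose of ALN-GO1". Quarterly placebo patients use the same rule for their single open-label dose.
- Quarterly patients randomized to ALN-GO1: the single-blind part ends at the Day 85 visit, and "the total ALN-GO1 treatment duration is Day 169 visit date".
- Placebo in either regimen: "treatment duration of placebo is min (first dose date of open-label ALN-GO1 or visit date of Day 85 visit".

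These ends match the treatment periods in SAP 7.2.3, where for monthly dosing "Day 85 is the end of treatment period" and for quarterly dosing "Day 169 is the end of open-label treatment period for 2-doses ALN-GO1 patients".

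For Part A, SAP 7.4.2 adds that "The actual dose administered and the number of injections will be summarized descriptively by dose level (or placebo) and overall". It states no equivalent for Part B, which has the duration summary, counts of patients with a missed dose or a dose interruption, and a listing of every administration. Continuous data are summarized "including the number of observations (n), mean, standard deviation, median, minimum, and maximum" (SAP 4.3). On missing data, "Only recorded (i.e. non-missing) data values will be used for reporting of descriptive statistics unless otherwise stated" (SAP 4.3.4).

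Protocol 4.7.3.3 asks patients who meet a stopping rule to finish the safety assessments, and Protocol 5.3.1 urges anyone who stops study drug to keep attending. On withdrawal, Protocol 5.3.2 seeks the EOT assessments. EOT is Day 57 in Table 2 (monthly), Day 141 in Table 3 (monthly open-label after placebo) and Day 85 in Table 4 (quarterly).

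**The concern.** An exposure summary should show how much study drug a group received. Where several doses are planned (monthly ALN-GO1, monthly placebo, monthly open-label, quarterly two-dose total), a visit date cannot show this, because the protocol keeps patients attending after dosing stops. The placebo minimum handles the switch to ALN-GO1, not stopping. Periods with one planned dose cannot be affected in this way.

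The second gap concerns patients without the end visit. A monthly patient who leaves before Day 85 has no Day 85 date, and the EOT visit does not supply one because it is Day 57 (or Day 141). A placebo patient who leaves before Day 85 has neither term of the minimum. The quarterly total, and the quarterly open-label duration after placebo, both need the study Day 169 visit. A patient who stays in the study but misses the end visit has the same problem.

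SAP 7.4 names exposure among the safety analyses, which serve the primary objective, and the SAP 7.2.3 layouts plan three single-blind ALN-GO1 patients per dose level. One patient can therefore move the summary visibly.

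**Working it through.** **Inputs.** Monthly doses on Days 1, 29 and 57; quarterly doses on Days 1 and 85 (SAP 7.4.2). Nominal visit days. Group sizes from the SAP 7.2.3 layouts. Duration = end day − first dose day + 1. The documents give no stopping rate, so what follows is scenarios.

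**Step 1: the plan's own figures.** SAP 3.3 and Protocol 4.2 give 57, 141 and 85 days. Counting to the last dose reproduces them: 57 − 1 + 1 = 57 (monthly ALN-GO1), 141 − 1 + 1 = 141 (monthly placebo then ALN-GO1), 85 − 1 + 1 = 85 (quarterly). For full courses SAP 7.4.2 gives instead 85 − 1 + 1 = 85 (monthly ALN-GO1), 169 − 85 + 1 = 85 (open-label after placebo) and 169 − 1 + 1 = 169 (quarterly total). These equal the last dose plus one interval: 57 + 28 = 85 and 85 + 84 = 169. The term treatment duration thus has two meanings in the documents.

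**Step 2: one patient who stops but attends the end visit.** The comparator, last dose plus one interval, is a convention and says nothing about how long the drug acts.

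| Doses received | SAP 7.4.2 | Last dose + interval |
|---|---|---|
| Monthly, 1 of 3 | 85 | 29 |
| Monthly, 2 of 3 | 85 | 57 |
| Monthly, 3 of 3 | 85 | 85 |
| Quarterly total, 1 of 2 | 169 | 85 |
| Quarterly total, 2 of 2 | 169 | 169 |

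**Step 3: effect on the summary.** One monthly patient stops after dose 1; the rest are fully dosed.

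| N | SAP mean | Mean under the convention | Mean doses of 3 |
|---|---|---|---|
| 3 | 85 | (2×85 + 29)/3 = 66.3 | 7/3 = 2.33 |
| 8 | 85 | (7×85 + 29)/8 = 78.0 | 22/8 = 2.75 |
| 16 | 85 | (15×85 + 29)/16 = 81.5 | 46/16 = 2.88 |

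The median is 85 throughout. The reported minimum is 85, against 29. For the quarterly total with one missed second dose, the reported mean is 169, against (2×169 + 85)/3 = 141 at N=3 or (5×169 + 85)/6 = 155 at N=6.

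**Step 4: no end visit (monthly, N=3, one leaver).** If a missing duration is dropped, the SAP summary is (85 + 85)/2 = 85 with n=2 in every case. With an end date for all three:

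- two doses, last contact Day 43: min(57, 43) = 43; mean (85 + 85 + 43)/3 = 71.0
- one dose, last contact Day 43: min(29, 43) = 29; mean 66.3
- three doses, last contact Day 70: min(70, 85) = 70; mean (85 + 85 + 70)/3 = 80.0

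**The case against.** The best defence is that the SAP figure is coherent as the length of the dosing period. SAP 7.2.2 defines that period by fixed days, and a quarterly placebo patient gets 85 days for a single ALN-GO1 dose. Calling 85 days too long for one monthly dose therefore needs a convention. This stands, so the 66.3 is only an illustration. Doses received needs no convention, and Part B does not summarize it.

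Other outputs do reveal stopping: the missed-dose and interruption counts, disposition, AEs leading to discontinuation, and the dosing listing. This also stands. For the quarterly open-label period, with one planned dose, the missed-dose table would show the shortfall directly if a discontinued dose is coded as missed, which the SAP does not say. None of these outputs corrects the duration.

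Shortening duration has side effects. It separates duration from the AE window, which for patients randomized to ALN-GO1 runs to Study Day 85 whatever was dosed. Within pooled placebo, one saline dose would count 29 days for a monthly patient who stops and 85 for a quarterly patient. Both objections stand, and the fix has to meet them.

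That leavers drop out of the statistic is a reading of SAP 4.3.4, which addresses unrecorded values and does not mention derived durations. The programming specification in SAP 8.2 is assigned output format, not this rule.

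A reader might infer that every early leaver lacks an end date. The documents do not support that. A quarterly ALN-GO1 patient who leaves after the Day 85 visit has a defined single-blind duration. For a quarterly patient who withdraws earlier, Table 4 combines Day 85 and EOT in one column, and it is unclear whether a withdrawal visit supplies the date.

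**Conclusion.** The point holds and is minor. For multi-dose periods the exposure summary cannot tell one dose from a full course if the patient attends the end visit, and no end date is stated when that visit is absent. In the smallest planned group, one patient stopping after the first of three monthly doses leaves mean and minimum at 85 while mean doses fall to 2.33. Under the stated convention the mean would be 22% lower (66.3/85 = 0.78) at N=3 and 4% lower (81.5/85 = 0.96) at N=16. These figures rest on nominal days and an assumed single early stop.

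A reader might infer that the safety findings are distorted. They are not: AE incidence counts patients in windows that do not use this duration, no hypothesis is tested, and no rate is divided by it. Nor do the figures show that 85 days overstates how long the drug acts; they concern dosing only.

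**What to change.** 1. Add a Part B summary of the number of doses received per patient, by period, regimen and dose level, including placebo. It also shows a skipped middle dose.
2. Label the present visit-based figure as the length of the dosing period, including the interval after the last dose, and cross-refer it to the 57, 141 and 85 days in SAP 3.3 and Protocol 4.2.
3. For treatment duration:
   - Last planned dose of the period given and end visit attended: keep the SAP's end date. For example, a last dose on Day 53 and an end visit on Day 89, both within the ±4-day windows, still give 89.
   - Last planned dose not given: end at the earliest of the SAP's end date, the last dose plus one scheduled interval (28 or 84 days, stated as a convention) and last contact.
   - Last planned dose given but end visit absent for any reason: end at the earlier of last contact and the nominal end day (Day 85 or 169). A monthly patient who misses Day 85 but attends Day 113 then counts 85.
   - Whether a withdrawal EOT visit is stored as Day 85 does not change these rules. Apply them separately to the quarterly single-blind period and the quarterly total.
4. State that AE windows stay as in SAP 7.2 and 7.4.1 and may be longer than treatment duration. Show placebo duration by regimen as well as pooled.

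The cost is SAP wording, one derivation and one small table from data already collected. Reported exposure will be lower if anyone stops early; for patients who are fully dosed and attend the end visit nothing changes.
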